5.5.1 Design (10 subjects)

5.5.2 Macronutrient microcapsules

- The microcapsules will be stored in line with manufacturer instructions.
- As the study drug will be blinded to the research investigator
- The Microcapsules will be introduced by the research nurse and labelled with the appropriate code drink A, B, C, D, E or F.
- It will be given at 9:00 am on an empty stomach prior to the meal.

5.5.3 Study procedures

At the screening visit a doctor or nurse will then perform the following tests and procedures to determine if the subject is eligible for the study:

- Medical history
- Physical examination
- Body measurements including height, weight and waist circumference
- Record of your medications or illnesses
- Urine pregnancy test (if applicable)

Visit 1-6 (1 week apart):

Subjects will be randomised to consume a one the 6 microcapsules in each week. Internet-based randomisation software will be used to allocate microcapsules to each subject at each visit

Eligible subjects will be invited to six consecutive visits in the clinical research centre at St Vincent University Hospital. On each occasion we would request you to have identical meals the night before between 19:00 and 20:00 hours and fast thereafter. Please refrain from alcohol and strenuous exercise for 24 hours before each study visit.

1. Food intake for the 24 h before each study day should be similar.
2. Participants will be asked to consume an identical meal between 19.00 and 20.00 on the night before each study (fish or pasta meal).
3. They will also be asked to be fasted and drink only water from 20.00 the night before the study.

In each visit, participants will be asked to be in the clinical research centre at 8:30. At 9:00 am a cannula will be inserted into the antecubital vein of the forearms. About 5 mL (1 teaspoon equivalent) will be taken to measure baseline hormone level. Another blood samples will be taken every 30 minutes thereafter. At 12:00, a final blood sample will be withdrawn and the cannula will be removed (total blood samples 7). They will be asked to answer a questionnaire regarding your feeling of hunger, satiety and if there is any nausea on a linear scale. Then a drink containing 200 grams of macronutrient microcapsules suspension equating to 1087 kcal will be offered. At 12:00 an *ad libitum* meal will be offered. After the meal they will also be provided with a similar questionnaire to fill in, in order to establish your fullness and satiety level. The total visit time is around five hours and there is a total of approximately 35 ml of blood (less than 2 table spoons) at each visit 1 to 6.

6 Methodology

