Methods: Ten healthy volunteers, aged 18 to 65 years will be recruited. Each subject will be studied on six occasions one week apart. Prior to each study day, the subjects will consume an identical meal between 19.00 and 20.00 on the night before and refrain from alcohol and strenuous exercise for the 24 hours before and after each study day.

Subject will arrive to the Clinical Research Centre at St Vincent University Hospital at 08.30 having fasted the night before from 20.00. At 9:00 am a cannula will be inserted into the antecubital vein of the forearms. About 5 mL (1 teaspoon equivalent) will be taken to measure baseline hormone level. Another blood samples will be taken every 30 minutes thereafter. At 12:00, a final blood sample will be withdrawn and the cannula will be removed (total blood samples 7).

They will be asked to answer a questionnaire regarding your feeling of hunger, satiety and if there is any nausea on a linear scale. Then a drink containing 200 grams of macronutrient microcapsules suspension equating to 1087 kcal will be offered.

In a randomized way all subjects will receive a mixed meal containing 200 grams of macronutrient microcapsules suspension equating to 1087 kcal in their successive weekly visits:

- Option 1 High protein mixed meal in capsules that break down in the stomach,
- Option 2 High protein mixed meal in capsules that break down in the distal small bowel,
- Option 3 High fat mixed meal in capsules that break down in the stomach,

- Option 4 High fat mixed meal in capsules that break down in the distal small bowel,
- Option 5 High CHD mixed meal in capsules that break down in the stomach,
- Option 6 High CHD mixed meal in capsules that break down in the distal small bowel.

After 3 hours (i.e. at 12:00) participants will be offered standard *ad libitum* meal to measure their food consumption and another blood sample will be drawn. All subjects will be asked to rate their appetite on a Visual Analogue Scale (VAS) (see appendix B). Upon VAS completion the subjects will be allowed to go home.

Blood sample will be withdrawn from participants at the beginning and at the end of each visit. These samples will be used to quantify gut hormone levels

Conclusion:

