5.2 Study design

This is a randomized six-way crossover study. The study will include 10 healthy volunteers with each subject being studied on six separate occasions at weekly intervals (Figure 3).

[figure not shown]

Figure 3: Schematic of Study Design

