6.3 Visit and procedures

Table 1: Schedule of Study Visits and Events

Trial Periods	Screening	V1	V2	V3	V4	V5	V6	Premature discontinuation	Follow up/ Premature discontinuation
Timing of visit (weeks)	-1	1	2	3	4	5	6		
Informed Consent	X								
Eligibility Assessment	X								
Record medications and illnesses	X							X	X
Anthropometric Measurements	X							X	X
Blood Samples		X	X	X	X	X	X		
Randomisation		X	X	X	X	X	X		
Visual Analogue Scales		X	X	X	X	X	X		
Adverse events		X	X	X	X	X	X	X	X

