6.3.2 Subsequent study visits

6.3.2.1 Study Visit 1 - 6 (Week 1 - 6)

- Record current and past medications and illnesses
- Randomisation to protein microcapsules or placebo
- Visual Analogue Scales

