Data will be analysed using GraphPad Prism (version 6.0) for Windows, GraphPad software (San Diego, CA, USA) and SPSS® (version 20.0) software (SPSS, Chicago, IL, USA). Central tendencies for patient and control group demographics, anthropometric data, caloric intake, VAS scores, QoL scores and macronutrient intake will be calculated and expressed using arithmetic mean \pm standard error of the mean or median (range), as appropriate. Differences in continuous variables between surgical and control groups will be calculated using the Student's *t* test or Mann-Whitney U test for parametric or non-parametric data, respectively. Correlative analyses will be performed using the Spearman Rho rank correlation to assess the relationship between *ad libitum* caloric intake and macronutrient intake with peri-operative weight loss and anthropometric data. Univariate analysis of factors associated with perioperative and post-surgical weight loss will be performed using Student's *t* test or one-way ANOVA for categorical variables or simple logistic regression for continuous variables. For the multivariate analysis, independent variables which were significant on univariate analysis, including standard demographic, oncologic and operative parameters as well as food intake and food preference, will be entered into a multiple logistic regression model with a forward stepwise selection procedure to assess their impact on perioperative and post-surgical weight loss. All statistical analyses will be two-tailed with the threshold of significance set at $P < 0.05$. Caloric intake and visual-analogue scores within groups will be compared by the Wilcoxon signed rank, matched-pairs test. Areas under the curve and plasma hormone levels will be compared by Wilcoxon rank-sum analysis.

12 Duration of Project

The estimated duration of the study will be 12 months. Screening and recruitment will begin in May 2017. Completion of the study is planned for May 2018.

13 Administrative considerations

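### Section 11 offers this six-drink crossover only a pairwise signed rank test for intake and VAS; a drink, visit and subject model on a balanced list would raise power from about 77% to 86% if drinks are equally variable

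*Combined protocol and SAP*

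**What the plan says.** **Design.** Section 5.2: "This is a randomized six-way crossover study", in 10 volunteers at weekly intervals. The Summary says "In a randomized way all subjects will receive a mixed meal" and lists six options: three macronutrient profiles, each with two release sites. None is a placebo. Section 5.5.2 has the drinks "labelled with the appropriate code drink A, B, C, D, E or F".

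**Allocation.** Section 5.5.3: "Internet-based randomisation software will be used to allocate microcapsules to each subject at each visit". The schedule in 6.3 ("Table 1: Schedule of Study Visits and Events") marks randomisation at each of V1 to V6. No sequence, square, block or order balance appears in the readable text. Figure 3, the design schematic, is not shown, and 5.5.1 is a heading without text.

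**Conflicting allocation.** Section 6.3.2.1, for the same visits: "Randomisation to protein microcapsules or placebo".

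**Analysis.** Section 11 refers to "Differences in continuous variables between surgical and control groups", which this trial does not have. Its only paired method is: "Caloric intake and visual-analogue scores within groups will be compared by the Wilcoxon signed rank, matched-pairs test". One-way ANOVA appears only for factors related to weight loss after surgery. No method has a drink, visit or subject term.

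**Size.** Section 5.5 derives n=10 from ad libitum energy intake at 80% power and alpha 0.05. It gives no effect size or SD. Section 11 makes all tests two-sided.

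**The concern.** Each volunteer supplies six measurements, but the signed rank test uses two of them per comparison. It estimates error from 10 differences and ignores what the other four drinks show about within-subject variability. It also cannot remove a drift over the six weeks, such as habituation to the test meal. Drift then adds noise to every difference, and more so when the order is not balanced.

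The stake is power in a trial sized at exactly 10 with no stated margin. A second matter is that 6.3.2.1 and the Summary disagree on what is randomised, so the comparison to be analysed is not fixed by the text.

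**Working it through.** **1. The plan's n=10.** It cannot be reproduced forward, because no effect size or SD is given. Solving backwards with a paired t test (9 df, two-sided 0.05, 80% power) gives an effect of 0.996 SD of the paired difference. The normal approximation gives (1.960 + 0.842)/√10 = 0.886. The effect 0.996 is used below as an assumption, with equal variance across drinks.

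**2. The planned test.** Exact signed rank at n=10 rejects at W ≤ 8 (true alpha 0.0488). Simulated power is 0.774, against 0.80 for the paired t.

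**3. The pooled model without trend.** Error df are (10−1)(6−1) = 45, or 45−5 = 40 with visit. The noncentrality is 0.996 × √10 = 3.150.
- Drink + subject, 45 df: power 0.869.
- Drink + visit + subject, balanced list, 40 df, variance factor 1.017: 3.150/√1.017 = 3.123, power 0.862.
- The same model on unrestricted random orders, average factor 1.128: 3.150/√1.128 = 2.966, power 0.825.

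**4. Adding a linear visit trend.** The documents give no trend, so d is an assumed range in SD of the paired difference per visit. Over the five steps from V1 to V6, d = 0.2 and 0.3 amount to 1.0 and 1.5 SD, which are large. Power from 5,000 simulations per cell:

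| Order and method | d=0 | 0.05 | 0.1 | 0.2 | 0.3 |
|---|---|---|---|---|---|
| Random, signed rank | 0.774 | 0.773 | 0.756 | 0.677 | 0.564 |
| Random, drink + subject | 0.870 | 0.861 | 0.851 | 0.778 | 0.676 |
| Random, drink + visit + subject | 0.826 | 0.820 | 0.833 | 0.829 | 0.834 |
| Balanced, signed rank | 0.777 | 0.773 | 0.751 | 0.684 | 0.570 |
| Balanced, drink + subject | 0.868 | 0.865 | 0.848 | 0.793 | 0.692 |
| Balanced, drink + visit + subject | 0.861 | 0.863 | 0.859 | 0.857 | 0.859 |

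**5. Splitting the gain.**
- Error pooling (row 2 minus row 1): 0.870 − 0.774 = 0.096 at d=0, and 0.851 − 0.756 = 0.095 at d=0.1.
- Balance plus visit term (row 6 minus row 2): −0.009 at d=0, +0.008 at d=0.1, +0.079 at d=0.2, +0.183 at d=0.3.

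If only the first visit differs, by 0.5 SD, power is 0.737 (signed rank, random order), 0.832 (drink + subject, random order) and 0.861 (full model, balanced list).

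**6. Why drift costs power.** In a random order of six, the visit gap between two drinks has variance 2 × (35/12) × (1 + 1/5) = 7. The variance of a paired difference is therefore multiplied by 1 + 7d²: 1.07, 1.28 and 1.63 at d = 0.1, 0.2 and 0.3. Over 10 subjects the mean gap has SD √(7/10) = 0.837 visits, and it reaches 1 visit or more in 26% of lists.

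**7. Type I error.** For signed rank under random order it is 0.050/0.048/0.046/0.046 at d = 0/0.1/0.2/0.3, so there is no inflation. A balanced list analysed by signed rank gives 0.045/0.038/0.030/0.015: it becomes conservative and gains no power. The balanced list with the full model gives 0.050/0.045/0.053/0.049.

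**8. Unequal variance.** Let the two compared drinks have r times the SD of the other four. The pooled error variance is then (2 + 4/r²)/6 times the right one.
- r = 0.75: 1.52. Simulated type I error 0.017 (30,000 runs). Power is about 73%, against about 77% for signed rank.
- r = 1.25: 0.76. Type I error 0.083.
- r = 1.5: 0.63. Type I error 0.117.

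**9. Feasibility of balance.** Ten is not a multiple of six, so exact balance for visit and preceding drink is impossible. Take the 6×6 Williams square built from 0,1,5,2,4,3 and repeat its rows 1, 2, 4 and 5. In the full square each drink's visit positions sum to 21. In the four added rows they sum to 14. The mean is (21 + 14)/10 = 3.5 for every drink.

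**The case against.** **The planned test is valid, and its shortfall is small.** Against the 80% implied by the sample size, signed rank at 77% is about 3 points short. The 9-point gap is measured against a stronger method that the plan never promised. This stands: the point is an efficiency gain, not an error in the test.

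**The model rests on similar variance.** Nothing in the documents shows that high-protein, high-fat and high-carbohydrate drinks vary equally. Step 8 shows that the model can lose to signed rank or exceed its nominal alpha. This stands too, and is why a paired test of the same two drinks must be pre-specified beside it.

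**Drift may be small.** The evening meal, fasting, alcohol and exercise are standardised, and the visits are a week apart. The primary endpoint and the hormone endpoint are changes, so a change from each visit's own baseline may partly cancel drift. The trend argument bears most directly on ad libitum intake. This stands; the case for balance and a visit term is as cheap protection.

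**Stronger readings to avoid.** A reader might infer that allocating at each visit contradicts a crossover, or means an independent draw each week. Sections 5.2 and the Summary imply that each subject takes every drink, and software that releases the next unused drink fits 5.5.3 and Table 1. A reader might also infer that no sequence exists. That cannot be known while Figure 3 is unseen.

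**Conclusion.** The concern holds as a worthwhile improvement and one clear contradiction. Section 11 was written for a different kind of study and gives this crossover no analysis of intake or VAS that uses all six drinks together. With equal variance and an effect of 0.996 SD of the paired difference, power is about 77% as planned and about 86% with a balanced list and a drink, visit and subject model.

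Almost all of that gain is error pooling and needs no trend. The balanced list and visit term are worth between −1 and +1 point at drifts of 0.1 SD per visit or less, 8 points at 0.2 and 18 at 0.3. It would be wrong to read the missing sequence as a source of bias or false positives, because random order protects against both.

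Separately, 6.3.2.1 and the six options in the Summary cannot both describe the randomisation, and they must be reconciled. Confidence in the size is medium: the effect, the equal variance and the drift are all assumed.

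**What to change.** 1. Reconcile 6.3.2.1 with the six options in the Summary.
2. For the six-drink crossover, randomise each subject once, before V1, to a pre-generated sequence of all six drinks, as balanced as n=10 allows. The Williams square plus its rows 1, 2, 4 and 5 is one example, with sequences assigned to subjects in random order. Later visits dispense the next coded drink. Amend 5.5.3 and Table 1 to match. If Figure 3 already shows a scheme, state it in the text.
3. In section 11, replace the text on surgical and control groups. Analyse intake and VAS with drink and visit as fixed effects and subject as random. Adopt the visit term and the balanced list together: a visit term on unrestricted random orders gives 82–83% instead of 86%, and balance without the term gains nothing.
4. Pre-specify a paired test of the same two drinks as a sensitivity analysis.

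**Cost.** A list generated in the same software and revised wording; no extra subjects or visits. The visit term uses 5 error df (45 to 40), and the package loses about 1 point of power against a drink + subject model if there is no trend. The plan should also state the reliance on similar variance. If the compared drinks have 1.25 (1.5) times the SD of the others, type I error is about 8% (12%). At 0.75 times it is about 2%, with power of about 73%, below signed rank.

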5.3 Primary endpoint

Changes in appetite as measured by visual analogue scale

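### In the readable text, appetite is rated only before the 9:00 drink and after the 12:00 ad libitum meal, so the primary VAS change does not isolate the satiety response to the drink

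*Combined protocol and SAP*

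**What the plan says.** Section 5.3 gives the primary endpoint in one line: "Changes in appetite as measured by visual analogue scale". It does not say which item, at what time, or how the ratings are summarised.

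The order of events has to be put together from three places.

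- **Section 5.5.2** times the drink: "It will be given at 9:00 am on an empty stomach prior to the meal".
- **Section 5.5.3** describes a first questionnaire, "They will be asked to answer a questionnaire regarding your feeling of hunger, satiety and if there is any nausea on a linear scale", followed directly by "Then a drink containing 200 grams of macronutrient microcapsules suspension equating to 1087 kcal will be offered". The ad libitum meal is offered at 12:00, and then: "After the meal they will also be provided with a similar questionnaire to fill in, in order to establish your fullness and satiety level".
- **Section 1 (Methods)** introduces the ad libitum meal with "After 3 hours (i.e. at 12:00) participants will be offered standard", next mentions a blood sample and an appetite VAS, and ends the visit with "Upon VAS completion the subjects will be allowed to go home".

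Table 1 and section 6.3.2.1 list the VAS once per visit without clock times. Section 6.4.4.4 describes the VAS as covering malaise, nausea and flushing, and the readable questions in Appendix B ask about anxiety, stress, sickness, dizziness and flushing. Section 11 compares VAS scores by the signed-rank test and mentions areas under the curve, without saying of what variable.

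**The concern.** Objective 2 asks for the satiety response to delivering macronutrients to the proximal or distal small bowel. Objective 3 separately asks how much is eaten afterwards. If the only rating after the drink follows the ad libitum meal, the primary endpoint mixes the two. A subject less sated by the drink can eat more and finish just as full, so two drinks could differ in satiety at 12:00 and look alike on the primary endpoint.

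Intake cannot simply be adjusted away, because it is itself affected by the randomised drink. A pre-meal rating that was never taken cannot be recovered by any later analysis. Hormones (Objective 1) and intake (Objective 3) are not touched, but VAS appetite is the named primary endpoint.

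**Working it through.** **1. Clock times** (sections 1, 5.5.2 and 5.5.3)

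| Event | Time | Minutes after drink | Appetite rating stated? |
|---|---|---|---|
| Arrival | 8:30 | −30 | no |
| Questionnaire, then drink | 9:00 | 0 | yes, before the drink |
| Blood draws every 30 min | 9:30 to 12:00 | 30 to 180 | none |
| Ad libitum meal offered | 12:00 | 180 | none stated before it |
| Questionnaire after the meal | no fixed time | 180 to about 270 | yes, after the meal |

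Draws at 9:00, 9:30, 10:00, 10:30, 11:00, 11:30 and 12:00 make 7. At about 5 mL each, 7 × 5 = 35 mL, which matches the volume in section 5.5.3. Six of the seven follow the drink, and none of those six has a stated appetite rating. Drink to meal is 12:00 − 9:00 = 180 min. Section 5.5.3 says "The total visit time is around five hours", so the visit ends near 8:30 + 5 h = 13:30, about 270 min after the drink. The post-meal rating therefore falls somewhere in a window of about 90 min.

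**2. How firm is this reading?** The paragraph in section 5.5.3 is not fully chronological: the first questionnaire is printed after the 12:00 draw and the removal of the cannula. The reading rests on the word that opens the drink sentence, on the explicit placing of the second questionnaire after the meal, and on the clock times. It does not rest on sentence order. Section 1 fits, since subjects leave once the VAS is done, but it does not itself say that the VAS follows eating.

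**3. What the change score measures.** For one subject and one drink, let S0 be the pre-drink rating, S1 the rating that would be given at 12:00 before eating, and M the further change produced by the meal. Then

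- pre-meal change = S1 − S0
- post-meal change = (S1 − S0) + M

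The contrast between two drinks on the post-meal change is Δ(S1 − S0) + ΔM. Objective 2 concerns the first term. M depends on how much is eaten, which is the outcome in Objective 3, so ΔM need not be zero. If subjects compensate by eating more after the less satiating drink, ΔM has the opposite sign to the first term. If all ate to the same fullness, the sum would be zero. The documents give neither the VAS spread nor the degree of compensation, so ΔM cannot be estimated.

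**4. Does the analysis section repair this?** No. Section 11 specifies no VAS time point and no pre-meal contrast, and its areas under the curve are not tied to VAS.

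**The case against.** The strongest reply is that this argues from silence in an incomplete copy. Figure 3, the design schematic, is not shown, and parts of the appendices are missing, so rating times could stand there. Section 11 lists areas under the curve separately from hormone levels, which may mean that serial VAS ratings were intended. This stands as a limit: the conclusion is conditional, and a reader should not infer that the plan rules out pre-meal ratings. The area-under-the-curve wording is weak evidence either way, because that section also speaks of surgical groups and perioperative weight loss, which this trial does not have.

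Second, Objective 2 gives no time window and the summary speaks of postprandial satiety, so a post-meal rating might be what was wanted. This stands in part. The randomised post-meal contrast is a valid comparison of the total effect after eating, and it would be wrong to call it biased for that quantity. But it does not separate response to the drink from response to the meal, and Objective 3 already treats what is eaten as a distinct outcome.

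Third, no loss has been shown. That is correct. A reader might infer lost power, but any figure would need an assumed fraction of the drink effect surviving the meal. The sample-size statement in section 5.5 does not help: it is based on ad libitum energy and gives no effect size or SD. A reader might also take the background study in section 2.1, where VAS fullness differed from 30 to 180 min after a test meal, as proof that the signal sits in the unrated window. That difference was between obese and normal-weight subjects, not between drinks, so it shows no loss here. The Figure 2 legend is closer: it describes a time course of hunger ratings after isocaloric high-protein, high-fat and high-carbohydrate meals. It is a precedent for rating over time, not a measure of what would be missed.

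**Conclusion.** The point holds, with medium confidence, for the text as it can be read. Appetite ratings are placed only before the 9:00 drink and after the 12:00 ad libitum meal, with none stated in the 180 minutes between, and section 5.3 fixes no item, time or summary. Unless Figure 3 or other unseen material schedules earlier ratings, the primary VAS change describes the total effect after a freely chosen meal and does not isolate the satiety response to macronutrient delivery. Differences between drinks could be masked; whether and by how much is unknown, and no loss of power is claimed.

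It still needs action before data collection. Even if pre-meal ratings are scheduled elsewhere, sections 5.3 and 5.5.3 do not say so.

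**What to change.** 1. **Section 5.5.3:** add a hunger and satiety VAS at 12:00, immediately before the ad libitum meal. If one is already scheduled elsewhere, state its time here.
2. **Instrument:** use the same named appetite items as in the pre-drink questionnaire, and list them in section 6.4.4.4 and Appendix B, whose readable text names none.
3. **Section 5.3:** define the primary endpoint as the change from the pre-drink rating to the 12:00 pre-meal rating, on the named item or items.
4. **Post-meal VAS:** keep it as a separate secondary or descriptive outcome, at a stated time after the meal.

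Ratings at each existing 30-minute draw are optional. If they are adopted, a baseline-adjusted area under the curve from 0 to 180 min could be the single pre-specified primary summary instead.

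**Cost.** The minimum is 1 scale × 6 visits = 6 per subject, × 10 subjects = 60 in total, filled in while subjects are already on site. The optional series is 6 × 6 = 36 per subject, × 10 = 360 in total, including the 12:00 rating. Both need protocol and CRF wording and add a little data entry. A rating just before the meal may draw attention to hunger, but equally under all six drinks.
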